The cornerstone of management for both entities is to delay therapy until progression to MM, at which time patients have overt end-organ damage.^{8,9} It is therefore unsurprising that patients with MGUS and SMM report high levels of anxiety and distress about their conditions,¹⁰ and cure is seldom achieved.¹¹ However, this paradigm may change as there are already clinical trials that show that early use of MM therapies in the precursor setting may alter the natural history of the disease¹², and importantly, may improve survival.¹³ For example, in a randomized open-label phase 3 trial¹³, 119 patients with high-risk smoldering myeloma were randomized to treatment or observation. Patients in the treatment group received an induction regimen (lenalidomide at a dose of 25 mg per day on days 1 to 21, plus dexamethasone at a dose of 20 mg per day on days 1 to 4 and days 12 to 15, at 4-week intervals for nine cycles), followed by a maintenance regimen (lenalidomide at a dose of 10 mg per day on days 1 to 21 of each 28-day cycle for 2 years). The primary endpoint was time to progression to symptomatic disease. Secondary endpoints were response rate, overall survival, and safety. After a median follow-up of 40 months, the median time to progression was significantly longer in the treatment group than in the observation group (median not reached vs. 21 months; hazard ratio for progression, 0.18; 95% confidence interval [CI], 0.09 to 0.32; $P < 0.001$). The 3-year survival rate was also higher in the treatment group (94% vs. 80%; hazard ratio for death, 0.31; 95% CI, 0.10 to 0.91; $P = 0.03$). A partial response or better was achieved in 79% of patients in the treatment group after the induction phase and in 90% during the maintenance phase. Toxic effects were mainly grade 2 or lower. Early treatment for patients with high-risk smoldering myeloma delays progression to active disease and increases overall survival. (NCT00480363).

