3. PARTICIPANT SELECTION

3.1 Eligibility Criteria

3.1.1 Diagnosed with high-risk MGUS or low-risk SMM⁶³ defined below:

Higher-Risk MGUS: bone marrow plasma cell concentration <10%# AND either serum M-protein level ≥ 1.5 g/dL to <3 g/dL, abnormal free light-chain (FLC) ratio (<0.26 or >1.65), or IgA MGUS.

Note: individuals with an abnormal FLC ratio that are classified as light-chain only are eligible. Light-chain only patients are defined as complete loss of immunoglobulin heavy-chain, accompanied by abnormal FLC ratio with an increased level of the appropriate involved light-chain (increased kappa FLC in patient with ratio >1.65, and increased lambda FLC in patients with ratio <0.26).

Low-Risk Smoldering Myeloma: bone marrow plasma cells $\geq 10\%$ # with the absence of additional high-risk features, which are further defined in the exclusion criteria (3.2.1)⁶⁴

#A new bone marrow biopsy is preferred for plasma cell determination at screening; however, determination of eligibility can be made from most recent bone marrow biopsy performed as long as it was within 2 years of enrollment.

3.1.2 Absence of evidence of CRAB criteria* or new criteria of active MM or active WM which including the following (note if one or more criteria has not been evaluated (e.g., no MRI), the criteria for active MM or WM for that feature is considered unmet):

- Increased calcium levels (corrected serum calcium >0.25 mmol/dL above the upper limit of normal or >0.275 mmol/dL) related to MM
- Renal insufficiency (attributable to MM)

- Anemia (Hb 2g/dL below the lower limit of normal or <10g/dL) related to MM
- Bone lesions (lytic lesions or generalized osteoporosis with compression fractures)
- Bone marrow plasma cells $\geq 60\%$
- Serum involved/uninvolved FLC ratio ≥ 100 , provided the absolute level of the involved free light chain is at least 100 mg/L and repeated twice (light chain smoldering myeloma as described in section 2.4 is not an exclusion criteria).
- MRI with two or more focal lesion that is at least 5 mm or greater in size
- Hyperviscosity symptoms per WM guidelines for symptomatic WM

**Participants with CRAB criteria that are attributable to conditions other than the disease under study may be eligible*

3.1.3 At least 18 years of age.

3.1.4 Eastern Cooperative Oncology Group (ECOG) performance status of 0, 1, or 2.

3.1.5 The following laboratory values obtained prior to the first dose of study drug/placebo:

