5.4 Prohibited Medications and Procedures

There are several medications and procedures which may increase the risk of lactic acidosis associated with metformin. Medical records will be reviewed for potential metformin contraindications including but not limited to the following: acetazolamide (Diamox), dichlorphenamide (Keveyis), methazolamide, topiramate (Topamax, in Qsymia), or zonisamide (Zonegran). In addition, participants will be advised to tell the study team if they plan to have surgery or any medical procedures requiring iodinated contrast agents, which can also increase the risk of lactic acidosis. In the event of a surgery or procedure that requires a contrast agent, participants will be advised to stop taking study medication 48 hours prior to the procedure and to refrain from re-starting study medication until they have undergone a blood test showing normal kidney function.

Participants are also prohibited from taking any investigational medications, or any cancer directed therapy during the study. In the event that a cancer-directed therapy is clinically warranted (e.g., progression to MM), participants will come off study so that appropriate care can be received.

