5.7 Removing a Participant from Treatment (Off Treatment)

Duration of therapy will depend on individual response, evidence of disease progression and tolerance. In the absence of toxicity or withdrawal from therapy, treatment may continue for up to 6 cycles when each cycle is defined as 28 days (or 12 cycles for those in the crossover arm), or until one of the following criteria applies:

- Disease progression to overt MM
- Intercurrent illness that prevents further administration of treatment
- Unacceptable adverse event(s) or co-morbid condition
- Participant demonstrates an inability or unwillingness to comply with the oral medication regimen and/or documentation requirements
- Participant decides to withdraw from the protocol therapy
- General or specific changes in the participant's condition render the participant unacceptable for further treatment in the judgment of the treating investigator

Participants will be removed from the protocol therapy when any of these criteria apply. The reason for removal from protocol therapy, and the date the participant was removed, must be documented in the case report form (CRF). Alternative care options will be discussed with the participant.

When a participant is removed from protocol therapy and/or is off of the study, the participant's status must be updated in OnCore in accordance with [REGIST-OP-1](#).

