5.9 Removing a Participant from Study (Off Study/Off Follow Up)

Participants will be removed from study when any of the following criteria apply:

- Lost to follow-up
- Withdrawal of consent for data submission
- Death
- Progression to overt MM

The reason for taking a participant off study, and the date the participant was removed, must be documented in the case report form (CRF). In addition, the study team will ensure the participant's status is updated in OnCore in accordance with [REGIST-OP-1](#).

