Partial Response (PR)	
$\geq 50\%$ reduction of serum M-protein.
 
If only measurable parameter is serum immunoglobulins free light chain (FLC), EITHER of the following changes qualify as partial response:
 
 - A 50% decrease in the difference between involved and uninvolved FLC levels; OR - A 50% decrease in the level of involved FLC AND a 50% decrease (normalization) in the ratio of involved/uninvolved FLC
Stable Disease (SD)	Not meeting criteria for CR, VGPR, PR or progressive disease.
Progressive Disease (PD)	
$> 25\%$ increase of serum M-protein (which must also be an absolute increase of ≥ 0.5 g/dL). PD is also measured by an absolute increase in bone marrow plasma cells $> 10\%$. If only measurable parameter is serum immunoglobulins free light (FLC), either of the following qualify as progression:
 
 - 50% increase in the difference between involved and uninvolved FLC levels from the lowest response level, which must also be an absolute increase of at least 10 mg/dL; OR - 50% increase in the level of involved FLC AND a 50% increase in the ratio of involved/uninvolved FLC from the lowest response level.

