12.7 Analysis of Secondary Endpoints

The secondary endpoint of this trial will be changes in a variety of biomarkers detailed in section 1.2. Changes in continuous variable outcomes will be evaluated from baseline to follow-up in the two groups using a repeated measures mixed-effects model that accounts for the correlation between baseline and follow-up measures and is generally robust to missing data. The baseline value of the dependent variable and disease subtype will be included as covariates in the regression models. Group-by-time interaction terms will be included as fixed-effects in the regression model. Model fit will be assessed using standard methods. All primary analyses will utilize stratified testing and intention-to-treat methods.⁷²

For changes in gene expression patterns, the precise methods are subject to change pending advancements in technology, but a general overview is provided below:

Paired-ended reads will be aligned against UCSC hg19 human annotation using Tophat 2.0.10; read counts for each gene will be determined using HTSeq 0.5.4. A subset of cells with more than 100,000 total reads across all genes will be selected for further analysis (70-80% of cells). To determine population average gene expression, the read counts observed in each cell will be normalized by the effective library size, determined by edgeR ‘calcNormFactors’ method. NMF-based consensus clustering will be used to cluster all single-cell RNA profiles. We will use coexpression networks-based gene prioritization tool GRAIL (<https://www.broadinstitute.org/mpg/grail/>) to select the most promising genes using gene expression signature as seeds. Cufflinks and Cuffdiff will be used to identify differentially expressed genes between the treatment arms.⁷³

Metabolite features will be analyzed as measures of peak areas, which are proportional to feature concentration and can be compared for any given metabolite. The metabolite variables will be standardized to a mean of 0 and standard deviation of 1.

For optional treatment extenders, this analysis is exploratory. We will assess the proportion of participants who are willing to take metformin for an additional 6 months. We will also evaluate response, duration of response, and depth of response according to modified IMWG criteria, or by mass spectrometry assessment.

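### The response table in section 9.4.11 has no overt-myeloma criterion, so a treatment extender removed for overt myeloma can be scored as stable disease or even partial response

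*Combined protocol and SAP*

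**What the plan says.** **Removal rules.** Section 5.7 lists "Disease progression to overt MM" among the reasons to stop protocol therapy, and section 5.9 lists "Progression to overt MM" among the reasons to leave the study. Both require the reason and date on the case report form (CRF). Section 5.4 adds that when cancer-directed therapy becomes necessary, "participants will come off study so that appropriate care can be received". None of the three defines overt MM. The nearest descriptions are in section 2.2, where current practice is to "delay therapy until progression to MM, at which time patients have overt end-organ damage", and in the eligibility list of section 3.1.2.

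**Response table.** In section 9.4.11, PD is reached in one of three ways:
- M-protein rises by more than 25% and by at least 0.5 g/dL.
- Marrow plasma cells rise by more than 10% in absolute terms.
- Free light chains (FLC) rise as specified, but only where FLC is the sole measurable parameter.

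SD is defined as "Not meeting criteria for CR, VGPR, PR or progressive disease". There is no row for participants who cannot be evaluated.

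**Use of the table.** Section 12.7 labels the extender analysis exploratory and says: "We will also evaluate response, duration of response, and depth of response according to modified IMWG criteria, or by mass spectrometry assessment". It serves the last secondary objective in section 1.3, the response trajectory in those taking metformin for up to one year.

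**The concern.** Overt MM is the outcome the intervention is meant to prevent, and the protocol treats it as serious enough to end both treatment and participation. The table that summarises disease course in the extenders does not recognise it. An analyst who follows the table as printed must ignore the removal reason and classify on markers alone. If the markers have moved too little for PD, the participant falls into SD. If they have fallen by half or more, the participant is a responder.

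Duration of response has the same weakness. Section 12.7 names it without saying what ends it. If PD from the table ends it, a responder who develops overt MM through organ damage, without a qualifying marker rise, is still in response.

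The extension has no concurrent control and at most about 30 participants, the size of the metformin arm. A single case placed in the wrong row would visibly change the read-out.

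**Working it through.** The protocol states no figure that can be reproduced here. The check applies the table literally and then bounds how often the problem could arise.

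**1. Literal application.** Take a hypothetical participant with overt MM shown by organ damage, and classify on M-protein and marrow only.

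| M-protein, g/dL | Change | Marrow rise | Table as written | If overt MM counts as PD |
|---|---|---|---|---|
| 1.5 to 1.5 | none | none | SD | PD |
| 1.5 to 1.9 | +0.4, +27% | none | SD (below 0.5 g/dL) | PD |
| 2.5 to 3.0 | +0.5, +20% | none | SD (not above 25%) | PD |
| 1.5 to 0.7 | -0.8, -53% | none | PR | PD |
| 1.5 to 2.1 | +0.6, +40% | none | PD | PD |
| 1.5 to 1.6 | +0.1, +7% | 12 points | PD | PD |

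The result depends entirely on the markers. Four of these six constructed cases miss PD; this shows the mechanism and is not a frequency.

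**2. Rise needed for PD.** The required rise is the larger of 0.25 × baseline and 0.5 g/dL.
- Baseline 0.5: 0.5/0.5 = 100%
- Baseline 1.0: 0.5/1.0 = 50%
- Baseline 1.5: 0.5/1.5 = 33%
- Baseline 2.0 and above: the 25% rule governs

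Section 3.1.1 admits IgA MGUS and MGUS with an abnormal FLC ratio without a minimum M-protein, so low baselines will occur. Marrow is sampled only when done for routine care, so the marrow route to PD will often be unobserved.

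**3. Chance of at least one overt-MM event during the extension.**
- Section 2.1 gives general rates of 10% per year for smoldering MM and 1% per year for MGUS.
- Extenders have completed the 6-month assessments, and overt MM before then would have removed them. Only the 6-month extension counts.
- Assumption: half of the *n* extenders have smoldering MM.

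The probability of staying event-free for 6 months is 0.9^0.5 (smoldering MM) or 0.99^0.5 (MGUS). With n/2 of each:

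P(at least one) = 1 − (0.9 × 0.99)^(n/4) = 1 − 0.891^(n/4)

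- n = 10: 1 − 0.891^2.5 = 25%
- n = 20: 1 − 0.891^5 = 44%
- n = 30: 1 − 0.891^7.5 = 58%

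**4. Sensitivity, n = 20.**
- Smoldering share 20%: 1 − 0.9^2 × 0.99^8 = 25%.
- Smoldering share 80%: 1 − 0.9^8 × 0.99^2 = 58%.
- The MGUS stratum is higher-risk, and section 2.1 says risk in some patients may reach 58% over 20 years. A constant rate would be 1 − 0.42^(1/20) = 4.2% per year. With half smoldering, P = 1 − (0.9 × 0.958)^5 = 52%.

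These figures count every overt-MM event. Misclassification needs one whose markers also miss PD, a fraction the documents do not give.

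**The case against.** The strongest reply is that these texts do different jobs. Sections 5.7 and 5.9 are removal rules. Section 9.4.11 is a response scale, openly described as modified, for an analysis labelled exploratory. The removal reason and date go on the CRF, and section 5.8 follows disease events by record review for up to 5 years, so overt MM can be reported beside the table. All of this stands. It means the event is not lost from the data. It does not tell the analyst which row the participant goes in, and the printed rule can give a wrong one.

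Several stronger readings are tempting, and the documents do not support them:
- **Overt MM is always scored SD.** It is not. Participants whose markers cross the thresholds are PD.
- **One endpoint has two rival definitions.** A removal rule and a response scale are not the same endpoint. The defect is a missing link.
- **Section 3.1.2 defines overt MM.** That list, headed "Absence of evidence of CRAB criteria* or new criteria of active MM or active WM", serves eligibility. It includes items such as "Bone lesions (lytic lesions or generalized osteoporosis with compression fractures" and an FLC ratio of at least 100, but no text carries it into 5.7 or 5.9. An FLC ratio crossing 100 is therefore not shown to be a removal event.
- **The primary question is affected because it asks about stabilization.** Section 1.2 concerns M-protein concentration from baseline to 6 months, analysed by the mixed model of section 12.2. That analysis does not use this table.
- **A reported stable-disease rate would be inflated.** No such rate is planned. Section 12.7 names response, duration and depth.
- **Event risk should be counted over 12 months.** Extenders must be free of overt MM at month 6.

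One could also say that a response category presupposes a measurement, so unassessed participants would not be called SD. That is a sensible convention, but the table does not state it. The extension calendar schedules electrophoresis and light chains only at the end of extended cycle 6, so a participant removed earlier may have no value for that period.

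**Conclusion.** The point holds in a limited form. The PD row omits overt MM and SD is the remainder, so an extender removed under 5.7 or 5.9 can be scored SD or PR when the M-protein, marrow or FLC changes miss the PD thresholds. Overt MM would also not end a duration of response.

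The effect is confined to the exploratory extender analysis in section 12.7 and the response-trajectory objective in section 1.3. The primary analysis and sample size are untouched.

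The figures of about 25%, 44% and 58% for 10, 20 and 30 extenders rest on an assumed half-smoldering mix and the protocol's general rates. At those rates they are an upper bound on the chance of a misclassified case, because only events with sub-threshold markers are misclassified. Exclusion of high-risk smoldering MM (section 3.2.1) should lower them further, while a rate above 1% per year in the higher-risk MGUS stratum would raise the underlying event chance. The figure for 30 also requires every metformin participant to extend. The correction is still worth making, because it is cheap and one case matters in a group this small.

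**What to change.** Reconcile section 9.4.11 with sections 5.7 and 5.9 for analysis purposes, before treatment codes are released:
- State that a participant removed for progression to overt MM, as recorded on the CRF, counts as PD in the response and duration-of-response analyses whatever the marker change.
- Limit SD to participants with a post-baseline disease assessment. Every extender already has a 6-month assessment, so tie this to the period being reported.
- Add a row for participants who are not evaluable and keep them in the denominator.

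Using the recorded removal reason avoids having to adopt the section 3.1.2 list and leaves clinical criteria alone. The cost is a few lines of wording and a slightly less favourable extender read-out. No new data or procedures are needed.

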10. STUDY CALENDAR

Registration and randomization should be conducted within 28 days (4 weeks) of baseline assessments. The 3-month safety labs should ideally be performed within 7 days of scheduled day 84 (preferably before). End of study/6- (or 12-) month assessment should ideally be completed within 7 days of last dose of study drug for those who completed 6 (or 12) months of treatment, or for those who were not able to complete 6 months of treatment, within 7 days of the 6 month timepoint or as close as feasible. Assessments must be performed prior to administration of any study agent and only after signing consent unless done as part of standard of care procedure. Each cycle is defined as 28 days.

	Screening/ Baseline	Day 1	Day 7	End of Cycle 1 (Day 28)	Day 48 (Optional)	End of Cycle 3 (Day 84)	End of Cycle 6 (Day 168)	End of Study Visit ¹⁰	Survival Follow Up ¹¹	EDC Timepoints
Metformin/Placebo ¹		-----Day 1-168-----								Day 1-168
Informed consent	X									N/A
Telephone Drug Adherence /AE Collection ²			X	X	(X)	X		X		N/A
Questionnaire/Survey ³	X							X		Baseline and EOT
Demographics	X									Baseline
Serum or Urine Pregnancy Test (if applicable)	X									Baseline
Medical history	X									Baseline
Physical exam ⁴	X				(X)			X		Baseline and EOT
Vital signs (BP, respiratory rate, temperature)	X							X		Baseline and EOT
Height	X									Baseline
Weight	X							X		Baseline and EOT
Performance status	X							X		Baseline and EOT
CBC w/diff, plts ⁵	X				X			X		Baseline and EOT
Serum chemistry ⁶	X				X			X		Baseline and EOT
Serum Free Light Chains (SFLC) Serum Protein Electrophoresis (SPEP), Immunofixation (SIFX), and Quantitative Immunoglobulins	X							X		Baseline and EOT
Research Bone Marrow Aspirate and Core ⁷	X							X		If a bone marrow biopsy or aspirate is performed at any time during the study as part of SOC, it should be captured in Inform
Research Blood Collection ⁸	X							X		N/A
Adverse Event Collection ⁹		From Time of Informed Consent to 30 days from Last Dose of Metformin								Record related AEs in database only

Survival and Event Collection ¹¹				X	N/A
1 Enough drug will be supplied for 3 cycles at a time. Labs will be reviewed prior to shipment of any medication. Participants may be shipped drug directly to their home following local policy, and will be instructed to return any unused drug, empty bottles, and completed diaries in pre-labeled return packaging to the lead site if they do not present in person to clinic.					
2 Study staff will contact the participant on day 7, day 28, and Day 168 (+/-3 days) to document AEs and assess study adherence. Day 48 is optional at the discretion of the clinical team. AEs and adherence will also be assessed at the End of Study Visit. Generally, End of Study assessments will be done in person, and interim assessments will be made by telephone, however exceptions can be made given COVID-19 precautions.					
3 Questionnaires may be completed in person, through RedCap, by mail, or other acceptable method.					
4 Physical exams may be waived or modified due to COVID precautions or travel restrictions with approval from a study MD but if done, should include review of critical body systems.					
5 Labs will be drawn as part of routine care and may include WBC with differential, Hgb, platelet count and ANC, as determined by the patient's clinical team.					
6 Labs will be drawn as part of routine care, and may include sodium, potassium, chloride, bicarbonate, BUN, creatinine, calcium, glucose, albumin, ALT (SGPT), total protein, AST (SGOT), total bilirubin, magnesium, phosphorus, B2M, and LDH, as determined by the patient's clinical team. The only labs that are required at the 3-month timepoint are AST, ALT, bilirubin, creatinine, and glucose, to ensure patient safety. These select safety labs are also required to determine eligibility.					
7 Research bone marrow samples are not required but highly encouraged. If a bone marrow aspirate is performed at any time following consent, please refer to sample collection section 9.4 for biobanking protocols.					
8 Research blood sample collection at the time of routine clinical blood draw any time prior to treatment – Please refer to Sample Collection Table in section 9.4					
9 Adverse events should be collected up to 30 days after the last dose of study drug. Any event that is thought related to metformin should be followed until resolution or stabilization.					
10 End of Study assessments should ideally be done within 7 days of completing 6 months of treatment, or for those that were not able to complete 6 months of treatment, as close to the 6 month timepoint as possible, ideally within 7 days.					
11 Survival status and data relating to disease response, treatment and status may be collected for up to 5 years from end of treatment.					

CALENDAR FOR EXTENDED TREATMENT (CROSSOVER ARM)

DFCI Protocol #: 21-008

Version Date: 02AUG2022

	Optional Extended Treatment Period (Crossover Arm)	End of Extended Treatment Cycle 3 Safety Assessment 3 (Day 84)	End of Extended Treatment Cycle 6 follow up (Day 168)	EDC Timepoints
Metformin ¹	Day 1		336	Day 168
Telephone Drug Adherence/AE Collection ²		x		N/A
Physical exam ³		(X)	x	EOT
Vital signs (BP, respiratory rate, temperature)			x	EOT
Weight			x	EOT
Performance status			x	EOT
CBC w/diff, plts ⁴		x	x	EOT
Serum chemistry ⁵		x	x	EOT
Serum Free Light Chains (SFLC) Serum Protein Electrophoresis (SPEP), Immunofixation (SIFX), and Quantitative Immunoglobulins			x	EOT
Research Bone Marrow Aspirate and Core ⁶			x	If a bone marrow biopsy or aspirate is performed at any time during the study as part of SOC, it should be captured in Inform
Research Blood Collection ⁷			x	N/A
Adverse Event Collection ⁸				Record related AEs in database only
Survival and Event Collection ⁹				N/A

1 Enough drug will be supplied for 3 cycles at a time. Labs will be reviewed prior to shipment of any medication. Participants may be shipped drug directly to their home following local policy, and will be instructed to return any unused drug, empty bottles, and completed diaries in pre-labeled return packaging to the lead site if they do not present in person to clinic.

2 Study staff will contact the participant to document AEs and assess study adherence. AEs and adherence will also be assessed at the End of Study Visit (and 1-year follow up for extended treatment group). Generally, End of Study assessments will be done in person, and interim assessments will be made by telephone, however exceptions can be made given COVID-19 precautions.

3 Physical exams may be waived or modified due to COVID precautions or travel restrictions with approval from a physician investigator but if done, should include review of critical body systems.

4 Labs will be drawn as part of routine care and may include WBC with differential, Hgb, platelet count and ANC, as determined by the patient's clinical team.

5 Labs will be drawn as part of routine care, and may include sodium, potassium, chloride, bicarbonate, BUN, creatinine, calcium, glucose, albumin, ALT (SGPT), total protein, AST (SGOT), total bilirubin, magnesium, phosphorus, B2M, and LDH, as determined by the patient's clinical team. The only labs that are required at the 3-month timepoint are AST, ALT, bilirubin, creatinine, and glucose, to ensure patient safety.

6 Research bone marrow samples are not required but highly encouraged. If a bone marrow aspirate is performed at any time following consent, please refer to sample collection section 9.4 for biobanking protocols.

7 Research blood sample collection at the time of routine clinical blood draw any time prior to treatment – Please refer to Sample Collection Table in section 9.4

8 Adverse events should be collected up to 30 days after the last dose of study drug. Any event that is thought related to metformin should be followed until resolution or stabilization.

9 End of Study assessments should ideally be done within 7 days of completing 6 months of treatment, or for those that were not able to complete 6 months of treatment, as close to the 6 month timepoint as possible, ideally within 7 days.

